Study Rationale	
More than eight million Americans each year experience unstable housing and/or homelessness; this includes 44% of all adults seen at community health centers. The chronically homeless have a 5- to 10-fold increased risk of premature death and high health care costs (driven by acute emergency department and hospital visits). Diabetes prevalence is approximately the same among the homeless versus general population (8%), but people with type 2 Diabetes who experience Homelessness, herein abbreviated as DH, have worse glycemic control and are hospitalized for diabetes complications a decade earlier and with more frequency than their housed peers. Most DH are of minority race and/or ethnicity. Poor glycemic control can induce “metabolic memory,” or long-term vascular stresses which persist despite later glucose normalization. Managing diabetes while homeless presents a unique set of barriers including food insecurity, low social support, lack of safe medication storage/refrigeration. Almost half of people who are homeless have comorbid mental illness and/or substance use disorders. Prescription medications are a cornerstone in the management of type 2 diabetes and avoidance of complications. Diabetes medication adherence is low in housed populations, and limited evidence suggests it is as low or lower among DH; adherence is highly correlated with all-cause hospitalization and mortality. A tailored intervention to improve medication adherence in DH could have substantial public health impact through reduction of the disparities in morbidity and mortality faced by DH.
 
The study goal is to develop and pilot test a collaborative care intervention tailored to DH using motivational interviewing and psychosocial support to improve medication adherence. Our team’s central hypothesis is that medication adherence (and eventual glycemic control, health care use/cost) will improve with an intervention tailored to the unique context of DH.

Study Objective(s)	
Primary
 
 • To develop and pilot test a behavioral intervention tailored to DH using behavioral activation, motivational interviewing and psychosocial support to improve medication adherence 
Secondary
 
 • To improve diabetes control (HgA1c)
Test Article(s)	Behavioral intervention to support medication adherence

Study Design	Single arm treatment-development trial
Subject Population	We will enroll adults (age \geq 18 yrs.) with type 2 diabetes who are experiencing homelessness.
Key Criteria for Inclusion and Exclusion:	
Inclusion criteria:
 
 1. Age 18 yrs. or older 2. English-speaking 3. Homelessness by federal definition in the last 12 mo. 4. Self-reported diagnosis of type 2 diabetes, later verified in medical record 5. Plan to stay in local area or be reachable by phone for the next 16 weeks 6. Willingness to work on medication adherence and diabetes self-care 
Exclusion criteria:
 
 1. Inability to provide informed consent (e.g., presence of a legal guardian, prisoners) 2. Active psychosis or intoxication precluding ability to give informed consent 3. Pregnant or lactating females. 4. Patients who choose to opt out of research.
Number Of Subjects	
Total Number of Subjects: 15
 
Total Number at Hennepin Healthcare: Unknown
 
Total Number of Sites: 1 (Health Care for the Homeless)

Study Duration	
Each subject's participation will last 16 weeks.
 
The entire study is expected to last one year.

Study Phases	(1) Screening : screening for eligibility and obtaining consent, baseline assessment
Screening	
Intervention	(2) Intervention : study intervention with counselor support approximately weekly in-person and/or by phone x 12 weeks
Follow-Up	(3) Follow-up : final assessment
Efficacy Evaluations	
 • Self-reported medication adherence • Self-reported psychological wellness • Self-reported diabetes self-management, distress • Hemoglobin A1c measured by point-of-care fingerstick
Safety Evaluations	Not applicable in this single arm trial
Statistical And Analytic Plan	The primary endpoint of this study is the feasibility and acceptability of the program to participants in this treatment development phase. We will summarize themes in the end-of treatment interview, assess satisfaction via structured survey, and

assess treatment dose received via frequency, length, and type of communications with study staff.

We will conduct exploratory analyses on our eventual primary behavioral endpoint of medication adherence and compare this with change in our eventual primary clinical endpoint of point-of-care Hemoglobin A1c during this same time frame. We will refine our use of patient-reported outcomes and administrative claims data for use in the future, planned randomized pilot trial.

Data And Safety Monitoring Plan

[name] (PI) will work closely with study staff to monitor the quality of data collected at assessment. This treatment development study (N=15), does not meet NIH criteria requiring a Data Safety Monitoring Board (DSMB), however Drs. [name], [name], and [name] will oversee a detailed safety monitoring plan.

TABLE 1: SCHEDULE OF STUDY PROCEDURES

2 BACKGROUND INFORMATION AND RATIONALE

OVERVIEW

This protocol is part 2 of a set of studies with an overall goal to develop and pilot test a collaborative care intervention using motivational interviewing and behavioral activation alongside education and psychosocial support to improve medication adherence tailored to the experiences of people experiencing homelessness and diabetes (DH). Our team's central hypothesis is that medication adherence and diabetes self-care (and eventual glycemic control, health care use/cost) will improve with an intervention tailored to the unique context of DH.

This work builds upon part 1 (HSR#19-4622) during which we completed Aim 1 activities to develop the initial Diabetes Homeless Medication Support (D-Homes) treatment manual through focus groups with DH at various levels of glycemic control and interviews with their multi-disciplinary providers. Data from this phase has identified barriers and strategies for medication adherence, patient values regarding medication, and treatment preferences and informed development of this part 2 application.

This protocol addresses Aim 2, to test patient perceptions of the feasibility and acceptability of study procedures and refine the D-Homes treatment manual through test cases (n=15). With a hypothesis that the D-Homes manual and study procedures will be feasible and acceptable to DH as measured by self-report and post-treatment interview.

Eventually, part 2 will be followed by a fully randomized pilot study in concordance with study Aim 3, a fully randomized pilot trial. Approval of this activity from the IRB will be sought before these activities begin.

SIGNIFICANCE

Homeless people in the US face disproportionate risk for premature death in part due to poorly controlled chronic diseases including diabetes. One and a half million unique US adults access homeless shelters annually. However, the total number of people experiencing homelessness (Box) is likely much higher¹⁹ with an estimated 7 million additional people living “doubled up” with family/friends in 2014.²⁰ New data recently established that 44% of all adults, and 37% of adults with diabetes, at US community health centers experience unstable housing.^{3,4} All-cause mortality rates among people experiencing homelessness in the U.S. are 4.5 to 9.6-times higher than the general population. Premature death often results from preventable chronic diseases including diabetes (2%) and its related comorbidities, e.g. heart disease (16%).²¹

While diabetes *prevalence* among the homeless and general population is comparable (~8% in both),²² there is evidence indicating

Box. Defining Homelessness:

Many definitions of homelessness exist. We adopt that of the U.S. government which includes people who:

- Lack “fixed, regular, adequate nighttime residence”
- Stay at emergency shelters, temporary living facilities, other places not meant for human habitation
- Will imminently lose their primary residence

(HEARTH Act, 2011)

large disparities in diabetes *outcomes*. Patients with type 2 Diabetes who are Homeless, herein abbreviated DH, have worse glycemic control²³ and are hospitalized for diabetes-related complications a decade earlier than their housed peers.²⁴ New data finds unstably housed adults have over five times the odds of diabetes-related emergency or hospital visit.⁴ This is of particular concern given “metabolic memory,” **or long-term vascular stresses which persist after significant early hyperglycemia despite later glucose normalization.**²⁵ While homelessness and unstable housing are increasingly recognized for

their impact on diabetes control, including by the American Diabetes Association,^{26,27} there is a paucity of solution-driven research. Thus, there is an urgent need to develop novel treatments to improve glycemic control in DH as they move across the spectrum of unstable housing.

Medication adherence is a complex behavior critically linked to improved overall and diabetes-specific outcomes. The rate of adherence for all long-term therapies averages 50% in the general (non-homeless) U.S. population due to barriers at various levels including: (i) patient, (ii) medication/disease, (iii) system, and (iv) socioeconomic.²⁸ Among privately insured populations, non-adherence to diabetes and related cardiovascular medications is associated with poor disease control (e.g., higher hemoglobin A1c and blood pressure), as well as increased risk of all-cause mortality and visits to the hospital and emergency department, and total health care costs.^{29,30} In low-income populations, cost-related non-adherence is common,³¹ and non-adherence is correlated with poor glycemic control.³² In fact, every 10% improvement in diabetes medication adherence reduced hemoglobin A1c by 0.16%.³³ *The importance of medication adherence is recognized by NIH with an active FOA to improve medication adherence (PA-18-722).*³⁴

Poor diabetes outcomes among the homeless is caused by low medication adherence. Non-adherence to medications across disease types is a known concern for homeless people especially when they are young (age <40 yrs.), have comorbid mental health/substance use disorders, experience food insecurity³⁵ and frequent the emergency department. Despite high rates of overlapping **physical and behavioral co-morbidities**,³⁶ 36% of US homeless adults report unmet needs for prescription medications.³⁷ Small studies find lower medication adherence in homeless patients when directly compared to housed peers.³⁸ DH patients specifically report challenges obtaining, storing, and retaining medication (especially insulin), and stigma surrounding the possession/use of needles.^{39,40,41,42}

[figure not shown]
Existing evidence-based models targeting medication adherence to improve diabetes will be the starting point for our novel intervention. We will draw from such interventions which target patient and system-level factors⁴³ to improve diabetes self-care activities, including medication adherence, for historically disadvantaged groups. The overarching theoretical model guiding treatment development is the **Information Motivation Behavioral Skills model**.⁴⁴ Our proposed treatment is also consistent with the **Collaborative Care Model**, a care management approach designed for individuals with multiple chronic conditions with known success improving diabetes outcomes in patients with depression.^{45,46} The Collaborative Care Model frequently uses Motivational Interviewing as the counseling approach, as we plan to in this study.⁴⁷ **Behavioral Activation (BA)** is another counseling approach that complements motivational interviewing. Behavioral intervention is empirically supported to address medication adherence in a population with high levels of underlying psychiatric disease (especially depression) and/or psychosocial stress.⁹⁶⁻⁹⁹ BA is easier to train than other empirically-supported counseling treatments and can be delivered with fidelity by bachelor's level practitioners.¹⁰⁰⁻¹⁰¹ BA is appropriately complemented by motivational interviewing, a person-centered, evidence-based approach to behavior change focused on participants' values and preferences and overcoming expected ambivalence to change.⁴⁸ It is particularly appealing to groups with historic disadvantage and minority race,⁴⁸ including the homeless,⁴⁹ and has improved medication adherence in non-homeless people with diabetes^{50,51} including when delivered by trained, non-mental health professionals to low-income populations.⁵² We will use BA first and employ MI when participants demonstrate ambivalence to change.

We will also integrate education using content consistent with the latest diabetes care guidelines.²⁶ And we will offer problem-solving to address psychosocial needs (including food and housing) modeled after clinic-based approaches for homeless veterans.^{53,54} *These evidence-based interventions*

offer a starting point for a new intervention which will be tailored to the unique context of DH through the iterative, multi-stakeholder process described below.

2.1 Name and Description of Intervention

The behavioral intervention tested in this protocol is the Diabetes-HOmEless Medication Support (D-HOMES) program. This will be a 12-week in-person, video, and/or phone-based support program centered on providing diabetes education, motivational and goal-setting support, and resource and care coordination (Figure 2). Psychological approaches of behavioral activation and motivational interviewing will be used along with provision of educational materials and tools to support behavior change, see Section 3. for details.

2.2 Selection of Treatment Dosages

Treatment doses are similar to a multiple health behavior change intervention currently underway by [name] (“Development of an Integrated Depression and Behavioral Risk Factor Reduction Intervention for Secondary Prevention following Acute Coronary Syndrome,” 1R03HL136540), primary mentor on this study. This is also in line with current literature about behavioral interventions to support improved diabetes self-management via medication adherence and psychosocial wellness.⁹⁴ During this treatment development phase we will monitor and adjust the number and duration of planned sessions based on the data from case study participants. This will inform Aim 3 randomized pilot future steps.

2.3 Relevant References See Section 10 for References.

2.4 Compliance Statement

This study will be conducted in full accordance of all applicable Hennepin Healthcare Research Policies and Procedures and all applicable Federal and State laws and regulations. All episodes of noncompliance will be documented and reported according to the Prompt Reporting Guidelines, Attachment EEE, of the Hennepin Healthcare IRB Policies and Procedures.

The investigators will perform the study in accordance with this protocol, will obtain informed consent and will report unanticipated problems involving risks to subjects or others and SAEs in accordance with The Hennepin Healthcare IRB Policies and Procedures and all Federal requirements. Collection, recording, and reporting of data will be accurate and will ensure the privacy, health, and welfare of research subjects during and after the study.

3 STUDY OBJECTIVES

The purpose of the study is to develop and pilot test a collaborative care intervention using motivational interviewing and behavioral activation alongside education and psychosocial support to improve medication adherence tailored to the experiences of people experiencing homelessness and diabetes (DH).

3.1 Primary Objective (or Aim)

The primary objective of this study is to determine whether a 10-session behavioral activation and motivational interviewing support program is feasible and acceptable to DH. The outcomes we will use to assess this treatment development phase of our work will be our ability to recruit and retain participants, the dose of treatment we can deliver (i.e., participant's attendance and follow-up with scheduled sessions and treatment activities), and participants' report of their satisfaction and overall experience during participation in a structured survey and qualitative interview.

3.2 Secondary Objectives (or Aim)

The secondary objectives will be to edit Aim 3 randomized pilot trial protocols and treatment manual instructions to optimally support participants. We will:

Clarify recruitment and retention strategies for DH

Assess the acceptability of patient-reported outcome measures and laboratory testing protocols

Finalize plans to use administrative claims and health care record data

Determine adequate incentive amounts and adequate timing of distribution

Refine protocols for distribution of phones and other tools to support intervention participation and behavior change

4 INVESTIGATIONAL PLAN

4.1 General Schema of Study Design

This is a single arm pilot trial to inform development of the D-HOMES behavioral treatment, see Table 1 above. The intervention, see Figure 1 above, targets diabetes education, motivation and goal-setting support, as well as resource and care coordination for people experiencing type 2 diabetes and homelessness (DH). The goal of this treatment development phase of our work is to refine approaches and protocols for further study of our program.

4.1.1 Screening Phase and Baseline Assessment

Recruitment protocols are summarized in section 9.5 below but will involve (1) invitation to aim 1 research participants who indicated interest in future research, and (2) referral from Health Care for the Homeless, Hennepin Healthcare, or shelter staff, (3) snowball sampling using advertisements and referrals via community partners and previous participants, (4) community advertisement using flyers in places such as bus stops, libraries, and shelters, and if needed (5) invitation letters and follow-up calls to eligible patients at Hennepin Healthcare, (6) tabling events with study flyers and snacks at Hennepin Healthcare or Health Care for the Homeless facilities and in public community spaces such as libraries, shelters, and community organizations.

Potential subjects will be screened by phone using the protocol inclusion and exclusion criteria. See Appendix A.

Congruent with other trials in this area,⁴⁹ we will conduct a 2-week run-in period to ensure participants are able to follow-up. During this time two baseline assessment visits will be scheduled. The second baseline assessment visit will be scheduled to correspond to the first treatment visit whenever possible.

4.1.2 Study Intervention

This study will be offered to willing participants as an adjunctive to usual diabetes care. During the screening and run-in period, participants will be encouraged and supported to continue seeing their regular health care team. If they do not have one, support will be given to help the participant schedule a primary care or endocrinology appointment at Hennepin County Health Care for the Homeless, Hennepin Healthcare, or another clinic/health system per participant preference.

4.1.3 Follow-up

To be eligible for follow-up, subjects must either have completed their planned coaching sessions or requested to end their coaching sessions early. Since the emphasis of this treatment development study is feasibility and acceptability, those ending early will be given particular attention so that their insights and experiences can shape future adaptations to the intervention and study design.

4.2 Allocation to Groups and Blinding *Not applicable to this phase of the study.*

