4.3 Study Duration, Enrollment and Number of Sites

4.3.1 Duration of Study Participation

Participants will be screened and recruited for a 2 week run-in period. They will engage in 10 weekly sessions over 12-weeks with our interventionist (“diabetes wellness coach”), and they will have a 4 week period within which to complete any missed visits and their final assessment visit. This is a maximum of 16 weeks duration per participant.

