Psychological approaches of behavioral activation and motivational interviewing will be used along with provision of educational materials and tools to support behavior change. Tools/materials will be distributed with travel and cell phone minute renumerations as above. See Appendix F for a sample list of tools and educational materials that might be provided. Which tools and educational materials are given to which participants will be decided by the coach depending on participant need as well as the specific goals that are mutually set. E.g.) A participant with 10 medications per day may benefit from a pillbox with AM and PM slots. E.g.) A participant with many appointments for behavioral and physical health care may benefit from a pocket calendar. Financial value of gifts ranges from \$2.99 (hand sanitizer) to \$32.95 (lock boxes).

In order to facilitate follow-up with this population, we will ask participants to provide multiple modalities by which we may contact them, including phone, email, and social media.

While study visits may occur by phone, email and social media communications will be limited to content only related to arranging details of when/where and how to connect with

participants. This may involve coordinating details to give a participant a study phone. This is necessary since we anticipate participants will have a higher than average likelihood of their phone service ending due to unpaid bills. If phone service is shut off, email and social media platforms continue to be used by participants through the phone's wifi capabilities. Participants will provide their email addresses, usernames and preferred platforms and provide signed consent to be contacted in these ways. Privacy concerns and appropriate use of email and social media to arrange for other communication with study team will be noted in the consent.

We will also ask participants to identify two people who know them well and would know how to reach them in the event that we are not able to contact them by phone, email, or social media. Similarly, we will ask participants to identify medical and social service providers who would know their current address or have up-to-date contact information for them. Participants will be asked to sign appropriate releases of information to allow medical and social service providers to share this information with the study team.

5.2.1 Visit 1

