5.2.6 Final Assessment

The final assessment visit will be completed within 4 weeks of completion of visit 10 or upon early termination. This will be completed by a research staff member who is distinct from the interventionist. The staff person will assess:

- Vital Signs: BP, HR
- Height and Weight
- Hemoglobin A1c
- Medication review
- Self-report survey measures
- Satisfaction with intervention

5.3 Part 2 of the Study *Details of Part 2 of the study (Aim 3 randomized trial protocols) will be submitted in a future amendment.*

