5.6 Rescue Medication Administration *Not applicable in this behavioral trial.*

5.7 Subject Completion/Withdrawal

Subjects may withdraw from the study at any time without prejudice to their care. They may also be discontinued from the study at the discretion of the Investigator for lack of adherence to study treatment or visit schedules and AEs. If the Investigator becomes aware of any serious, related adverse events after the subject completes or withdraws from the study, they will be recorded in the source documents and on the case report form.

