5.7.1 Early Termination Study Visit

Any participant who withdraws will have no further study visits.

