Satisfaction with intervention	
At the final assessment visit, the assessor (who is not the interventionist) will collect input about the participant's experiences during the intervention.
 
Participant satisfaction will be assessed by the Client Satisfaction Questionnaire, an 8-item measure developed in the mental health field,⁹⁵ and a qualitative interview focused on experiences during participation from screening through final assessment visit. See interview guide in Appendix I

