6.3 Pharmacokinetic Evaluation *Not applicable*

6.4 Safety Evaluation

Subject safety will be monitored by adverse events and rates of early termination of the study. We will also follow safety protocols in case we identify dangerous blood pressure, or heart rate values at baseline or final assessment visits. See Section 8 for details.

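### Section 4.1.3, followed as written, bars investigator-discontinued participants and silent non-attenders from the only visit that collects CSQ-8 and the exit interview; early termination and withdrawal are not kept apart

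*Combined protocol and SAP*

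**What the plan says.** Section 4.1.3 states who may enter follow-up: "To be eligible for follow-up, subjects must either have completed their planned coaching sessions or requested to end their coaching sessions early". It adds that early leavers deserve special attention because their experience should shape the intervention. The synopsis describes the follow-up phase as the final assessment, so this condition governs that visit.

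Three other sections bear on the same visit:

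- Section 5.2.6: "The final assessment visit will be completed within 4 weeks of completion of visit 10 or upon early termination". It does not say who must have ended participation.
- Section 5.7.1, which is titled as the early termination visit: "Any participant who withdraws will have no further study visits".
- Section 5.7 lets participants withdraw at any time. It also allows them to be "discontinued from the study at the discretion of the Investigator for lack of adherence to study treatment or visit schedules", and allows discontinuation for adverse events.

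Section 6.4 adds: "Subject safety will be monitored by adverse events and rates of early termination of the study". Section 7.2 lists withdrawal as part of a safety and tolerability endpoint.

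On satisfaction, 6.1 says: "At the final assessment visit, the assessor (who is not the interventionist) will collect input". That input is CSQ-8 and the qualitative interview, and 7.1 makes both part of the primary endpoint. Section 7.3.2 promises intent-to-treat analysis and gives no rule for missing data.

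**The concern.** Acceptability is half of the primary endpoint, and its structured measures come from a single visit. A rule that admits completers and people who ask to stop, but not people who drift away or are removed for poor attendance, decides who can speak to acceptability by how they left. Those omitted are among the people 4.1.3 says it wants to hear from.

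The wording also leaves staff without one instruction. Early termination leads to a visit in 5.2.6, while the section titled for it in 5.7.1 allows none after withdrawal. Early termination and withdrawal are themselves reported outcomes (6.4, 7.2), so each needs a single meaning before it can be counted.

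**Working it through.** The plan gives no figure to reproduce. Section 7.4 justifies the sample size in words only, without a dropout rate. The check is to follow each exit route through the three sections.

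| Exit route | 4.1.3 | 5.2.6 | 5.7.1 |
|---|---|---|---|
| Completed planned sessions | Eligible | Visit | Not addressed |
| Asked to end coaching, stays in study | Eligible | Visit | Not addressed |
| Stopped attending, no request | Not eligible | Unclear: no section says when silence becomes termination | Not addressed |
| Discontinued by investigator, non-adherence | Not eligible | Visit if read as an eligibility rule; silent if read as timing | Not addressed unless this counts as withdrawal |
| Discontinued by investigator, adverse event | Not eligible | As above | As above |
| Withdrew from the study | Eligible only if leaving counts as asking to end coaching | Visit if early termination includes withdrawal | No visit |

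**What depends on this visit.** CSQ-8 and the exit interview (6.1), the post-treatment surveys (6.1), and the closing point-of-care A1c and vital signs (5.2.6, 6.2).

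**What does not.** Recruitment, session attendance and contact counts (7.1, 7.3.2), claims data and record-abstracted A1c (6.1), and session recordings and notes (7.3.2, 9.2).

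**Coverage.** With N = 15 (synopsis), one unassessed person is 1/15 = 6.7%. If m people fall outside 4.1.3, final-visit data can cover at most (15 − m)/15. The values of m are assumptions:

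- m = 1: 14/15 = 93%
- m = 3: 12/15 = 80%
- m = 5: 10/15 = 67%

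Section 4.3.2 allows enrolment to stop before 15, in which case each person weighs more. These figures show the most that coverage could be under 4.1.3. They are not what a reworded rule would regain, because some people could not be reached under any rule, and some who are reached would say they want to stop and so already qualify.

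**Cost per added visit.** Section 9.7.2 pays $45 for the final assessment, and the text of 9.7.1 gives $10 travel per visit: $45 + $10 = $55. The table in 9.7.1 shows $20 in the final-visit column. Its total of $140 equals 12 × $10 + $20, so it holds only one $20 item, and that may be the bonus for completing all 10 sessions. If it is travel, the cost is $45 + $20 = $65. For 1 to 5 added visits the range is 1 × $55 = $55 to 5 × $65 = $325.

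**The case against.** The strongest reply is that the sections can be read together. Section 5.2.6 may state only when the visit happens, with 4.1.3 deciding who gets it. Ending coaching (4.1.3) may differ from leaving the study (5.7.1), and 6.4 does refer to termination of the study. This stands in part. A reader might infer that 5.2.6 flatly contradicts 4.1.3 for investigator-discontinued participants, but the documents support that only if 5.2.6 is an eligibility rule. The same condition applies to withdrawals: 5.2.6 and 5.7.1 collide only if early termination includes withdrawal. The timing reading does not help the excluded groups, however, because it leaves 4.1.3 in control and 4.1.3 shuts them out. Nor does the protocol ever state the distinction between coaching and study.

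The second reply is that few people would be affected. Section 5.2 sets up tracing: "We will also ask participants to identify two people who know them well and would know how to reach them". Section 4.3.1 gives slack: "they will have a 4 week period within which to complete any missed visits and their final assessment visit". Section 2.2 lets the number of planned sessions be adjusted. Someone who is traced and says they want to stop then qualifies. This stands and shrinks the silent group, but it does nothing for those the investigator has discontinued.

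The third reply is that session recordings and notes keep some account of the experience of people who leave. That is correct, although they do not replace CSQ-8 or an exit interview with someone other than the coach.

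A reader might also infer that satisfaction will look better than it is. The documents do not support this. Section 4.1.3 includes people who ask to stop, and section 5.2 expects phone service to lapse for unpaid bills, so silence need not mean dissatisfaction.

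**Conclusion.** The restriction in 4.1.3 is real and should be fixed. As written, it makes investigator-discontinued participants and silent non-attenders ineligible for the only visit that yields CSQ-8, the exit interview and the final-visit measures. They are ineligible, not missing after an attempt. Intent-to-treat cannot be met for visit-based outcomes on those terms. Separately, early termination needs one definition across 5.2.6, 5.7.1 and 6.4.

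The size is 6.7% of a sample of 15 per person left out. The number of such people is unknown. No direction or size of bias in CSQ-8 or A1c is claimed, and the feasibility measures of recruitment, attendance and contact are intact. The point does not invalidate the study. It rests on the prose sections, because the body of Table 1 and the separately attached appendices were not available for this review and could bear on the visit.

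**What to change.** 1. Reconcile 4.1.3, 5.2.6 and 5.7.1 by defining two separate states: coaching has ended, and the participant has withdrawn from the study or declines contact. Use the same terms in 6.4 and 7.2.
2. Reword 4.1.3 so that the final assessment is offered to every enrolled participant with confirmed diabetes (5.1.2) whose coaching has ended, including through non-attendance or investigator discontinuation for non-adherence, unless they withdraw or decline contact. The sponsor should state when non-attendance counts as coaching having ended, solely so that the offer has a trigger.
3. For participants discontinued because of adverse events, reconcile the same passages and leave to the investigator whether an assessment is attempted. Discontinuation and safety rules stay unchanged.
4. Report CSQ-8, interview and final-visit results as the number assessed out of all enrolled, by exit category: completed, asked to end coaching, stopped attending, discontinued for non-adherence, discontinued for adverse events, withdrew. Show run-in losses separately.
5. Reconcile the intent-to-treat sentence in 7.3.2 by labelling the pre-post tests as analyses of those assessed.

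The cost is wording in a few sections, one reporting table, some staff time for tracing through contact routes already collected, and about $55 in payments per added visit ($65 at most). No new instruments or participants are needed.
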